3.1 Study design

This is a 20-week, randomized, double-blind, 3-arm, placebo-controlled, parallel-group, multicenter study of Secukinumab (AIN457) to examine the clinical response as measured by the ASAS20 and the NSAID-sparing effect of Secukinumab treatment. The clinical efficacy (ASAS20 response) and the cumulative NSAID sparing effect of two strategies of NSAID tapering after initiation of Secukinumab will be evaluated as compared to placebo:

Patients will be randomized 1:1:1 to one of the following treatment groups:

- Secukinumab delayed NSAID tapering: Secukinumab 150 mg s.c. at weeks 0, 1, 2, 3, 4, 8, 12, 16 and 20 with placebo injections at Week 5, 6, 7 and 17, 18, 19 to maintain the blind.
- **Secukinumab early NSAID tapering:** Placebo at weeks 0, 1, 2, 3 to maintain the blind; followed by Secukinumab 150 mg s.c. at Week 4, 5, 6, 7, 8, 12, 16 and 20 with intermittent Placebo injections at week 17, 18, 19 to maintain the blind.
- **Placebo:** Placebo at weeks 0, 1, 2, 3, 4, 5, 6, 7, 8 and 12. After the Week 16 assessments of the secondary endpoint have been performed, these patients will receive Secukinumab 150 mg s.c. at weeks 16, 17, 18, 19 and 20.

The patients will be stratified at randomization according to their status of prior TNF α inhibitor exposure, i.e. TNF α inhibitor naive patients or TNF α inhibitor inadequate responders (TNF α -IR). The only condition that will be placed on enrollment targets for each stratum is that no less than 60% of patients (122 patients) are TNF α inhibitor naïve, i.e., no more than 40% of patients (82 patients) are TNF α -IR. In theory the percentage of TNF α inhibitor naïve patients could reach 100%, although that is not anticipated.

All patients will be advised to continue on the maximum recommended/tolerated dose of NSAIDs for the first 4 weeks of the trial.

A follow-up visit is to be done 4 weeks after last study treatment administration for all subjects, regardless of whether they complete the entire study as planned or discontinue prematurely.

NSAID tapering strategy

All patients will be advised to taper/discontinue their NSAID intake starting at Week 4 to Week 20. Patients may use NSAIDs on an on-demand basis to avoid an unacceptable worsening of disease activity.

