Week	-10 to -4	-4 to -2	BSL	1	2	3	4	5	6	7	8	12	16	17	18	19	20	F24
Adverse events/SAEs (if applicable, including injection site reactions) ⁷	X																	
NSAID intake reported in eCRF		Χ	Х	Х	Х	Х	Х											X
Provide NSAID Diary to patient and instruct patient							Х				Х	х	Х					
NSAID intake captured in patient diary								х	х	Х	Х	х	Х	х	Х	х	Х	
Check NSAID diary									Х		Х	Х	Χ				Χ	
Patient's global assessment of disease activity (VAS)			x	х	X		x		x		X	X	X				X	х
Patient's assessment of back pain intensity (VAS)			х	х	х		х		Х		Х	х	Х				Х	х
BASFI			Х	Х	Х		Х		Х		Х	Х	Х				Х	Х

	Scree	ning ¹																
	Screening Visit 1	Screening Visit 2		Treatment 1										Follow Up				
Week	-10 to -4	-4 to -2	BSL	1	2	3	4	5	6	7	8	12	16	17	18	19	20	F24
BASDAI			Х	Х	Х		Х		Х		Х	Х	Х				Х	Х
Spinal mobility (BASMI Linear + chest expansion)			х		Х		х				х	х	х				Х	
SF-36			Х				Х					Х					Х	
ASAS Health Index			Х				Х					Х					Х	
Erythrocyte Sedimentation Rate (ESR)		Х	х		Х		х				Х	х	х				Х	х
High sensitivity C-reactive protein (hsCRP)		Х	х		Х		Х				х	х	х				Х	х
HLA-B27			Х															

¹ If the patient's washout period ≤ 4 weeks, Screening visit 1 (SV1) and Screening visit 2 (SV2) can be performed on the same day.

² Eligibility and relevant medical history assessments are conducted at SV1, SV2 and Baseline (BSL) / Day 1'. The data for all three visits should be recorded on the corresponding eCRFs available at SV1.

³ The following eCRFs are to be completed: AS Disease background eCRF, Modified New York criteria for AS eCRF

⁴ These assessments are source documentation only and will not be entered into the eCRF.

⁵ The PPD skin test can be performed at any time during the Screening period, but it must be read within 72 hours and before randomization.

	Scree	ening ¹																
	Screening Visit 1	Screening Visit 2					Treat	tment	:1					Tre	eatment	2		Follow Up
Week	-10 to -4	-4 to -2	BSL	1	2	3	4	5	6	7	8	12	16	17	18	19	20	F24

⁶ A chest X-ray or MRI is required if it was not performed and evaluated within 3 months prior to Screening. The X-ray should be performed after it is certain the patient meets inclusion/exclusion criteria in order to minimize unnecessary exposure to radiation. The X-ray may be replaced by an MRI assessment.

⁷ AEs/SAEs occurring after the patient has signed the informed consent must be captured on the appropriate eCRF page. SAEs must be recorded from signing of informed consent, AEs must be captured from the BSL visit on.

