#### Treatment arms

Patients will be randomized 1:1:1 to one of the following treatment groups:

- **Secukinumab - delayed NSAID tapering:** Secukinumab 150 mg s.c. at weeks 0, 1, 2, 3, 4, 8, 12, 16 and 20 with placebo injections at Week 5, 6, 7 and 17, 18, 19 to maintain the blind.
- **Secukinumab – early NSAID tapering:** Placebo at weeks 0, 1, 2, 3 to maintain the blind; followed by Secukinumab 150 mg s.c. at Week 4, 5, 6, 7, 8, 12, 16 and 20 with intermittent Placebo injections at week 17, 18, 19 to maintain the blind.
- **Placebo:** Placebo at weeks 0, 1, 2, 3, 4, 5, 6, 7, 8 and 12. After the Week 16 assessments of the secondary endpoint have been performed, these patients will receive Secukinumab 150 mg s.c. at weeks 16, 17, 18, 19 and 20.

The patients will be stratified at randomization according to their status of prior TNF $\alpha$  inhibitor exposure, i.e. TNF $\alpha$  inhibitor naïve patients or TNF $\alpha$  inhibitor inadequate responders (TNF $\alpha$ -IR). The only condition that will be placed on enrollment targets for each stratum is that no less than 60% (i.e. 114) of patients are TNF $\alpha$  inhibitor naïve, i.e., no more than 40% (i.e. 76) of patients are TNF $\alpha$ -IR. In theory the percentage of TNF $\alpha$  inhibitor naïve patients could reach 100%, although that is not anticipated.

For primary analysis both the secukinumab treatment arms will be pooled and compared against placebo.

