	secukinumab 150 mg s.c. (early tapering) vs. placebo.
To evaluate change in patient reported neck, back and hip pain (BASDAI question 2; Appendix 4) from baseline on a continuous basis in patients randomized Secukinumab 150 mg s.c. (Secukinumab from week 0 with NSAID tapering allowed from week 4; “delayed tapering”) vs. placebo from week 0 to week 12.	Mean change in patient reported neck, back and hip pain score (BASDAI question 2) from baseline for secukinumab 150 mg s.c. (delayed tapering) vs. placebo from baseline (week 0) to week 12.
To evaluate change in patient reported neck, back and hip pain (BASDAI question 2; Appendix 4) from baseline on a continuous basis in patients randomized Secukinumab 150 mg s.c. (early tapering) vs. placebo from week 0 to week 16.	Mean change in patient reported neck, back and hip pain score from baseline for secukinumab 150 mg s.c. (early tapering) vs. placebo from week 0 to week 16.
To compare ASAS20 response rates at week 4 in Secukinumab 150 mg. s.c. (Secukinumab from week 0 with NSAID tapering allowed from week 4; “delayed tapering”) vs. week 20 in the patients switching from Placebo after 4 weeks of Secukinumab exposure each.	Proportion of patients fulfilling ASAS20 criteria at week 4 for secukinumab 150 mg s.c. (delayed tapering) vs. week 20 in patients switching from placebo after weeks of secukinumab exposure.
To explore the total ASAS-NSAID [Area Under Curve (AUC)] Score from treatment start with Secukinumab to a Secukinumab exposure of 12 weeks.	Total ASAS-NSAID [Area Under Curve (AUC)] Score for both secukinumab arms from week 0 to week 12 for secukinumab 150 mg s.c. (delayed tapering) and from week 0 to week 16 for secukinumab 150 mg s.c. (early tapering).
To explore the total ASAS-NSAID [Area Under Curve (AUC)] Score from Week 4 to Week 16 for each treatment arm.	Total ASAS-NSAID [Area Under Curve (AUC)] Score for each treatment arm from Week 4 to Week 16.
To explore the efficacy of secukinumab based on the proportion of patients with no NSAID intake after Secukinumab exposure of 12 weeks.	Proportion of patients with no NSAID intake at week 12 for secukinumab 150 mg s.c. (delayed tapering) and at week 16 for secukinumab 150 mg s.c. (early tapering).
To explore the efficacy of Secukinumab 150 mg s.c. in patients with no NSAID intake at week 12.	Proportion of patients with no NSAID intake at week 12 for each treatment arm.

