## 2.13 Other Exploratory analyses

All the exploratory efficacy evaluation will be performed on FAS population. Refer to [Table 1.2-1](#) of Section 1 for the list of exploratory endpoints.

The following exploratory efficacy variables will be summarized on the FAS for all applicable analysis visits unless otherwise specified.

1. Total ASAS-NSAID [Area Under Curve (AUC)] Score from treatment start with Secukinumab to a Secukinumab exposure of 12 weeks.
2. Total ASAS-NSAID [Area Under Curve (AUC)] Score From Week 4 to Week 16
3. Proportion of patients with no NSAID intake after Secukinumab exposure of 12 weeks
4. Proportion of patients with no NSAID intake at week 12.
5. Change from Baseline in the ASAS Health Index after Secukinumab exposure of 12 weeks
6. Change from Baseline in the ASAS Health Index at week 12
7. Change from baseline in BASMI
8. ASAS40 response
9. ASAS20 response
10. ASAS5/6 response
11. Change from baseline in hsCRP
12. Change from baseline in total BASDAI
13. BASDAI 50 response

14. ASAS partial remission
15. Change from baseline in ASAS components including:
  - Patient global disease activity
  - Total spinal pain
  - Inflammation (average of BASDAI questions 5 and 6)
  - BASFI
16. Change from baseline in ASDAS-CRP and ASDAS-ESR
17. ASDAS inactive disease as defined by  $ASDAS < 1.3$
18. ASDAS clinically important improvement (change in  $ASDAS \geq 1.1$ ) and major improvement (change in  $ASDAS \geq 2.0$ )
19. Reasons given in the patient diary on why he was not able to taper NSAIDs despite reduced spinal pain

All endpoints relating to exploratory objectives will be summarized descriptively. Summary statistics will include absolute frequencies and percentages for the categorical variables and the number of patients (n), minimum, mean, median and maximum for continuous variables. Change from baseline will also be presented for some exploratory variables based on the the endpoints mentioned in section 1 Table 1.2-1. Graphical representation will also be performed if required.

The following exploratory endpoints will also be summarized categorically as absolute and relative frequencies (proportions, %).

- Proportion of patients fulfilling ASAS20 criteria at week 4 for secukinumab 150 mg s.c. (delayed tapering) vs. week 20 in patients switching from placebo after weeks of secukinumab exposure.

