### 5.5.7 ASAS-NSAID Score

The recommendations by ASAS (Dougados 2010) will be used to score each patient's NSAID use during specific time periods. The components that go into the calculation of the score is the type of NSAID, average daily dose, length in days of the time period of interest and the number of days with NSAID intake within the time period of interest. The final score should be between 0 and 100 but can in rare cases be larger than 100.

The scoring of NSAIDs is described below.

Score	Intake
0	No intake
100	150 mg diclofenac, 600 mg etodolac, 150 mg indometacin, 20 mg piroxicam, 1000 mg naproxen, 90 mg etoricoxib, 200 mg ketoprofen, 20 mg tenoxicam, 200 mg aceclofenac, 200 mg flurbiprofen, 15 mg meloxicam, 400 mg celecoxib, 2400 mg ibuprofen, 400 mg phenylbutazone.

The CRF provided dose information will be handled as follows:

- Doses > maximum dose will be scored as > 100
- Missing doses will be scored with maximum daily dose for the current NSAID (i.e. score of 100)

Drug start and end dates are needed in order to know the number of days an NSAID was prescribed. In case they are missing, the following rules will be used:

- Missing start dates will assume the start date of medication is Day -28 (i.e. prior to start of study drug)
- Missing end dates will assume the end date of medication is the patient's last day in the Study

- If the study drug is ongoing when the patient discontinues then the drug end date will be equal to the day of discontinuation. The period end date will also end on the day of discontinuation

The table below presents the score associated with the dosing frequency as specified by the ASAS definition and how the different database entries will be categorized. The frequency was not consistently specified in the ASAS publication, the below categorization was selected.

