**Table 5-2 Mapping of dosing frequency to NSAID score**

Frequency	Scores	Database entry
Patient did not take any NSAID during the period of interest	0/7	
<1 day/week	0.5/7	Q2W, MISSING, PRN, UNK, ASNEEDED, QM, Q4W, Q3W
≥1 – <3 days/week	2/7	Q1W, WEEKLY, BIW
≥3 – <5 days/week	4/7	TIW, QIW
≥5 – <7 days/week	6/7	
Everyday	7/7	TID, BID, DAILY, Q24H, QID, QD
Note: Q2W=every 2 weeks, PRN=as needed, UNK=unknown, Q1W=one a week, BIW=twice a week, TIW=three times a week, TID=three times a day, BID=twice a day, QIW= four times a week, Q24H=QID=QD=one a day, QM=one a month; Q4W=one every 4 weeks; Q3W=one every 3 weeks.		

To calculate the NSAID cumulative score the following formula will be used for each NSAID being taken:

$100 * (\text{Daily dose} / \text{pre-specified max dose}) * \text{frequency score} * (\text{min}(\text{medication end date, period end date}) - \text{max}(\text{medication start date, period start date}) + 1 = \text{range of days patient used the medication}) / \text{number of days the patient was in the period.}$

In case a patient takes more than one type of NSAID, changes the dose or the frequency of NSAID during the period of interest, additional scores will be calculated for each new combination and the final score for that patient is the sum of all scores.

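### The early-arm ASAS-NSAID AUC window opens four weeks before secukinumab starts, and the early-arm Week 16 ASAS Health Index endpoint has no scheduled data

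*SAP*

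**What the plan says.** **AUC.** The objective in SAP Table 1.2-1, item 1 of SAP section 2.13 and protocol exploratory objective 6 all define the AUC "Score from treatment start with Secukinumab to a Secukinumab exposure of 12 weeks". The endpoint cell beside that objective gives Weeks 0 to 12 for the delayed arm and "from week 0 to week 16 for secukinumab 150 mg s.c. (early tapering" for the early arm. SAP section 1.1 gives early-arm dosing as "Placebo at weeks 0, 1, 2, 3 to maintain the blind; followed by Secukinumab 150 mg s.c. at Week 4" and later visits. Protocol section 3.1 adds: "All patients will be advised to continue on the maximum recommended/tolerated dose of NSAIDs for the first 4 weeks of the trial". The next row of Table 1.2-1 plans a separate AUC, the "Score for each treatment arm from Week 4 to Week 16".

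The only NSAID formula is in SAP section 5.5.7, where it is called a cumulative score. It divides by the "number of days the patient was in the period", and the section says "The final score should be between 0 and 100", with rare exceptions above 100. It does not mention an AUC.

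**Week 16 quality-of-life entries.** Table 1.2-1 sets the Health Index endpoint after 12 weeks of exposure at Week 12 (delayed) and Week 16 (early). The underlying variable is protocol exploratory objective 10, repeated in protocol section 9.5.2 and SAP section 2.13 item 5. Protocol section 9.5.1 and SAP section 2.7.1 list SF-36 PCS at Week 12/16. Protocol exploratory objective 26 and the last row of Table 1.2-1 ask for a Week 12 (delayed) versus Week 16 (early) comparison on all objectives. In protocol Table 6-1, the SF-36 and "ASAS Health Index" rows are marked at baseline and Weeks 4, 12 and 20 only.

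**The concern.** Within one table row, the objective and the endpoint describe different windows for the early arm. A programmer working from the endpoint column would add four weeks of placebo on untapered NSAIDs to a quantity meant to describe intake during secukinumab exposure. Intake in that arm would look higher than the objective intends. NSAID sparing is a stated purpose of the trial, so the number will be read even though it is exploratory.

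The second problem is one of feasibility: an endpoint is dated to a visit at which the instrument is not scheduled. The output would be empty, or would be filled with a value from a different length of exposure.

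**Working it through.** **1. Window implied by the objective.** Rule: first secukinumab week to that week plus 12.
- Delayed arm: 0 to 0 + 12, Weeks 0 to 12. This reproduces the SAP cell.
- Early arm: 4 to 4 + 12, Weeks 4 to 16. The SAP cell says Weeks 0 to 16.
- Reading treatment start as the first study injection does not rescue the cell, because it gives Weeks 0 to 12.

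**2. Day counts.** Weeks 0 to 16 are 16 × 7 = 112 days; Weeks 4 to 16 are 12 × 7 = 84 days. The excess is 28 days, and 28/112 = 25%. This step needs no assumption.

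**3. Effect on the value.** Let B be the mean score over Weeks 0 to 4 and M the mean over Weeks 4 to 16.
- Per-day excess: (4B + 12M)/16 ÷ M − 1 = 0.25 × (B/M − 1).
- Excess as a sum: (4B + 12M)/(12M) − 1 = B/(3M).

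The intake curves below are assumptions. The fall of 63.9 is the protocol's planning value in section 9.7.
- *Main curve:* 100 to Week 4, linear to 36.1 at Week 12, then flat. Weeks 4 to 16: 8 × (100 + 36.1)/2 + 4 × 36.1 = 544.4 + 144.4 = 688.8 score-weeks, so M = 688.8/12 = 57.4. Weeks 0 to 16: 400 + 688.8 = 1088.8, or 1088.8/16 = 68.1 per day. Excess: +19% per day (68.1 vs 57.4), +58% as a sum (1088.8 vs 688.8).
- *Constant 100:* 100 vs 100 per day (0%); 1600 vs 1200 as a sum (+33%).
- *Start 70, same fall, to 6.1 at Week 12:* Weeks 4 to 16 sum to 8 × 38.05 + 4 × 6.1 = 328.8, so M = 27.4. Weeks 0 to 16: (280 + 328.8)/16 = 38.05. Excess: +39% per day.

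**4. Why the unit matters.** Give both arms the main curve. The delayed arm over Weeks 0 to 12 is 400 + 544.4 = 944.4, or 78.7 per day. With the cell as written, the early arm is higher as a sum (1088.8 vs 944.4) but lower per day (68.1 vs 78.7). With Weeks 4 to 16 it is lower on both scales (688.8 vs 944.4; 57.4 vs 78.7). Over the planned common window of Weeks 4 to 16, the two arms agree at 57.4.

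**5. Week 16 collection.** Counted by column, the Table 6-1 rows for SF-36 and the Health Index mark baseline and Weeks 4, 12 and 20. The BASDAI row, read the same way, does mark Week 16, which checks the count. Applying the rule in SAP section 2.1.2 for parameters not collected at every visit gives windows of Days 2–32 (Week 4), 33–99 (Week 12) and 100–165 (Week 20). There is no Week 16 window, so a value taken on Day 113 would be analysed as Week 20. Early-arm exposure from Day 29 is 113 − 29 = 84 days at Week 16 and 141 − 29 = 112 days (16 weeks) at Week 20.

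**The case against.** - **The right early-arm number is already planned.** The Week 4 to 16 AUC is the next row of Table 1.2-1. That stands and limits the harm, but the mislabelled output would appear beside it.
- **Weeks 0 to 16 might be deliberate.** The documents do not support this. SAP section 4 declares no change to protocol-specified analyses. Where Weeks 0 to 16 is meant for the early arm (BASDAI question 2, protocol exploratory objective 4), the objective says so.
- **A derivation exists.** Section 5.5.7 describes a cumulative score over a period of interest, so it would be wrong to say the SAP has no formula. What is missing is a statement that the AUC is this day-averaged score and not a sum.
- **The windows differ by design.** A reader might infer from 57.4 vs 78.7 that the exposure-window AUC should never be compared between regimens. The documents do not support that. Four weeks of secukinumab on stable NSAIDs define delayed tapering, and objective 26 asks for the equal-exposure comparison.
- **The distortion has no fixed range.** This stands. Baseline intake may be well below 100: entry needs only 50% of the highest recommended dose, and the SAP plans a subgroup with baseline score under 75. Only the day counts come from the documents alone.
- **SF-36 is a list slip.** This also stands. A reader might infer that an SF-36 endpoint is lost, but every dedicated SF-36 objective is at Week 12. Only the all-objectives comparison reaches Week 16.

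**Conclusion.** The early-arm AUC cell is wrong as written: 112 days instead of 84, with 25% of the window before any secukinumab. The effect on the value rests on assumed curves and on the unstated unit: +19% per day or +58% as a sum on the main curve, 0% or +33% with constant intake. The early-arm Week 16 Health Index endpoint cannot be produced from scheduled data.

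The point is minor. A reader might infer that the trial's conclusions are at risk, but they are not. The AUC and Health Index endpoints are exploratory and summarised descriptively (SAP section 2.13), and SF-36 PCS lies outside H1 to H11. No confirmatory test, type I error or sample size is affected.

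**What to change.** 1. Change the early-arm AUC cell in Table 1.2-1 to Weeks 4 to 16. State whether the AUC is the day-averaged score of section 5.5.7 or a sum.
2. Keep the equal-exposure comparison if wanted, with a note that the delayed window contains four weeks on stable NSAIDs by design and that the planned Week 4 to 16 AUC is the same-calendar comparison.
3. Drop the early-arm Week 16 Health Index endpoint, or re-date it to Week 20 and label it as 16 weeks of early-arm exposure. Make matching edits to protocol exploratory objective 10, protocol section 9.5.2 and SAP section 2.13 item 5.
4. Exempt the Health Index and SF-36 from the Week 12 versus Week 16 comparison (objective 26 and the last row of Table 1.2-1).
5. Delete the Week 16 part of the SF-36 PCS entry in protocol section 9.5.1 and SAP section 2.7.1.
6. Record the Health Index and comparison changes in SAP section 4, which now reads as not applicable.

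No new data or model is needed, and the corrected early-arm AUC equals a value already planned. The cost goes beyond SAP wording, because items 3 to 5 touch protocol text.

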Intra-articular corticosteroids are not permitted within the 4 weeks preceding randomization and up to Week 12. After Week 12, no more than 1 joint per 24-week period may be injected. No single injection should exceed 40 mg of triamcinolone (or equivalent) and the total dose of intra-articular corticosteroid may not exceed 80 mg of triamcinolone (or equivalent) during any 20-week period. Injection of intra-articular steroids is not permitted within 8 weeks prior to Week 20.

Non-steroidal anti-inflammatory drugs (NSAIDs) (including COX-1 or COX-2 inhibitors), low strength opioids and acetaminophen/paracetamol

Patients regularly using NSAIDs, low strength opioids, or paracetamol/acetaminophen should be on stable dose for at least 2 weeks before randomization to allow inclusion. They should remain on a stable dose in the study up to Week 4.

Changes in the NSAID intake will be captured by the patient in the patient diary and checked and be transferred into the eCRF at all scheduled study visits after week 4.

Patients taking low strength opioids or paracetamol/acetaminophen PRN within the 2 weeks before randomization can continue to do so in the study; however, they have to refrain from any intake during at least 24 hours before a visit with disease activity assessment.

After Week 12 assessments are completed, a change in the low strength opioids, or paracetamol/acetaminophen treatment regimen is permitted.

Any change of the low strength opioids, or paracetamol/acetaminophen treatment during the trial should be recorded on the appropriate Prior and Concomitant medication eCRF page.

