Automatic validation procedures within the system check for data discrepancies during and after data entry and, by generating appropriate error messages, allow the data to be confirmed or corrected online by the designated investigator site staff. The Investigator must certify that the data entered into the electronic Case Report Forms are complete and accurate. After database lock, the investigator will receive copies of the patient data for archiving at the investigational site.

8.3 **Database management and quality control**

Novartis staff / CRO staff review the data entered into the CRFs by investigational staff for completeness and accuracy and instruct the site personnel to make any required corrections or additions. Queries are sent to the investigational site using an electronic data query. Designated investigator site staff is required to respond to the query and confirm or correct the data.

Concomitant medications entered into the database will be coded using the WHO Drug Reference List, which employs the Anatomical Therapeutic Chemical classification system. Concomitant procedures, non-drug therapies and adverse events will be coded using the Medical dictionary for regulatory activities (MedDRA) terminology.

Laboratory samples will be processed centrally and the results will be sent electronically to Novartis (or a designated CRO).

ECG records will be kept at the site as source data.

Diary data will be entered into a paper diary by the patient. The study staff will check the diary and enter the data into the eCRF. The database will be sent electronically to Novartis (or a designated CRO).

Randomization codes and data about all study drug(s) dispensed to the patient and all dosage changes will be tracked using an Interactive Response Technology (IRT). The system will be supplied by a vendor, who will also manage the database. The database will be sent electronically to Novartis (or a designated CRO).

Each occurrence of a code break via IRT will be reported to the clinical team and monitor. The code break functionality will remain available until study shut down or upon request of Novartis.

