To evaluate secukinumab 150 mgs.c versus placebo in achieving an improvement in Ankylosing Spondylitis Disease Activity Score (ASDAS)-C-Reactive Protein (CRP) and ASDAS-Erythrocyte Sedimentation Rate (ESR)	Mean change from baseline in ASDAS-CRP and ASDAS-ESR for each treatment group.
To evaluate secukinumab 150 mgs.c versus placebo with ASDAS inactive disease as defined by ASDAS < 1.3	Proportion of patients with ASDAS inactive disease (i.e ASDAS < 1.3).
To evaluate secukinumab 150 mgs.c versus placebo in ASDAS clinically important improvement (change in ASDAS $\geq$ 1.1) and major improvement (change in ASDAS $\geq$ 2.0)	Proportion of patients with ASDAS clinically important improvement (change in ASDAS $\geq$ 1.1) and major improvement (change in ASDAS $\geq$ 2.0)
To assess overall tolerability and safety of Secukinumab at reduced NSAID intake.	Overall safety, as measured by frequency and severity of adverse events and changes in laboratory, vital signs and ECG values from baseline.
To evaluate the reasons given by the patient in the patient diary on why he was not able to taper NSAIDs despite reduced spinal pain.	Proportion of patients for each reason given in the patient diary on why he was not able to taper NSAIDs despite reduced spinal pain.
To compare the secukinumab arms (pooled Group1 and Group2) concerning ASAS20 response criteria after exposition of 12 weeks against placebo at week 12.	Proportion of patients fulfilling ASAS20 criteria in the pooled Secukinumab groups after exposure of 12 weeks (i.e. Secukinumab delayed tapering at week 12 and Secukinumab early tapering at week 16) and placebo regimen at Week 12.
To compare the secukinumab arms (pooled Group1 and Group2) concerning ASAS20 response criteria after exposition of 12 weeks against placebo at week 16.	Proportion of patients fulfilling ASAS20 criteria in the pooled Secukinumab groups after exposure of 12 weeks (i.e. Secukinumab delayed tapering at week 12 and Secukinumab early tapering at week 16) and placebo regimen at Week 16.
To compare the secukinumab arms (pooled Group1 and Group2) concerning ASAS-NSAID score after exposition of 12 weeks against placebo at week 12.	Total ASAS-NSAID score in the pooled Secukinumab groups after exposure of 12 weeks (i.e. Secukinumab delayed tapering at week 12 and Secukinumab early tapering at week 16) and placebo regimen at Week 12.

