### **2.8.1 Adverse events (AEs)**

The crude incidence of treatment emergent adverse events (i.e. events started after the first dose of study treatment or events present prior to the first dose of study treatment but increased in severity based on preferred term, and events until 30 days for AE and SAE after last dose of study treatment) will be summarized by primary system organ class and preferred term.

The summaries will be presented separately by study periods i.e. week 1-16 and after week 16.

In addition, exposure time-adjusted incidence rates including 95% confidence intervals will be provided for the entire treatment period to adjust for differences in exposure. A graphical display of the crude rates and exposure-adjusted incidence rates will be presented for all AEs and serious AEs by system organ class. A graphical display of relative frequencies within system organ classes and relative risks, as appropriate, will be presented.

Adverse events will be summarized by presenting, for each treatment group, the number and percentage of patients having at least one AE, having an AE in each primary system organ class and having each individual AE (preferred term).

The most common adverse events reported (>1 % in any group for each preferred term in the SOC-PT table or > 1 % in any group) will be presented in descending frequency according to its incidence in total secukinumab group (combining all secukinumab treatment groups) starting from the most common event.

Summaries (crude incidences only) will also be presented for AEs by severity and for study treatment related AEs. If a particular AE 'severity' is missing, this variable will be listed as missing and treated as missing in summaries. If a subject reported more than one adverse event with the same preferred term, the adverse event with the greatest severity will be presented. If a subject reported more than one adverse event within the same primary system organ class, the subject will be counted only once with the greatest severity at the system organ class level, where applicable.

Separate summaries will be provided for

- adverse events suspected to be related to study drug by the investigator
- deaths
- adverse events leading to discontinuation
- adverse events leading to temporary dose interruption.

The MedDRA version used for reporting the study will be described in a footnote.

Follow-up period summaries will be done for all patients in follow-up.

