## **2.8.4 Other safety data**

### **2.8.4.1 ECG and cardiac imaging data**

Not applicable.

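### Adverse event tables for the objective of safety at reduced NSAID intake are cut only at Week 16, so they mix four stable-NSAID weeks with tapering time; the endpoint also names ECG changes that have no data or analysis behind them

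*SAP*

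**What the plan says.** The exploratory objective in SAP Table 1.2-1 reads "To assess overall tolerability and safety of Secukinumab at reduced NSAID intake", and its endpoint is "Overall safety, as measured by frequency and severity of adverse events and changes in laboratory, vital signs and ECG values from baseline". The endpoint sets no time window. The windows come from SAP 2.8.1: "The summaries will be presented separately by study periods i.e. week 1-16 and after week 16". The same section plans exposure-adjusted AE rates for the entire treatment period. The treatment periods in SAP 2.1.1 also break only at Week 16.

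On NSAIDs, Protocol 3.1 says "All patients will be advised to continue on the maximum recommended/tolerated dose of NSAIDs for the first 4 weeks of the trial", and Protocol 5.5.7 says of regular users "They should remain on a stable dose in the study up to Week 4". Protocol 5.5.6 allows NSAID changes once the Week 4 assessments are done. Protocol 3.1 advises tapering in all three arms from Week 4 to Week 20, with on-demand use still permitted.

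Laboratory and vital-sign changes are summarised visit by visit (SAP 2.8.3, 2.8.4.2). SAP 2.8.3 also plans maximum change, most extreme shift and worst CTCAE grade over a whole period.

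On ECGs, footnote 4 to Protocol Table 6-1 says "These assessments are source documentation only and will not be entered into the eCRF". Protocol 8.3 adds "ECG records will be kept at the site as source data". SAP 2.8.4.1, headed "ECG and cardiac imaging data", is marked not applicable.

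**The concern.** The objective is about safety while NSAID intake is reduced. The main AE table starts at baseline, so it includes the four weeks in which NSAIDs are meant to be unchanged. In the early-tapering arm, patients in those weeks have neither secukinumab nor reduced NSAIDs. A between-arm AE difference that arises only under tapering is therefore averaged with time in which it could not arise.

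The trial hopes to support guidance on reducing NSAIDs after a biologic is started (Protocol 1.2). Its most relevant safety evidence is the randomised, placebo-controlled stretch in which every arm may taper, Week 4 to Week 16. No planned AE table isolates that stretch, although the SAP already uses this window for NSAID intake itself (the ASAS-NSAID area under the curve from Week 4 to Week 16).

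Separately, the endpoint promises ECG changes from baseline that the database will not hold.

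**Working it through.** The documents give no figure for this point, so there is none to reproduce. The check sets the schedule beside the planned tables and then does arithmetic on weeks.

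**Step 1. What each period contains** (Protocol 3.1, 5.2, 5.5.6).

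| Period | Delayed arm | Early arm | Placebo arm | NSAIDs |
|---|---|---|---|---|
| Weeks 0-4 | secukinumab | placebo injections | placebo | stable |
| Weeks 4-16 | secukinumab | secukinumab | placebo | tapering allowed |
| After Week 16 | secukinumab | secukinumab | secukinumab | tapering allowed |

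Only the middle row has both a placebo control and permission to taper. The planned AE tables merge the first two rows, or all three for the exposure-adjusted rates.

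**Step 2. Share of stable-NSAID time**, assuming full follow-up.
- AE table to Week 16: 4/16 = 25%.
- Whole treatment period: 4/20 = 20%.
- Two secukinumab arms together to Week 16, one patient from each (32 weeks): secukinumab with tapering allowed 24/32 = 75%; secukinumab with stable NSAIDs 4/32 = 12.5%; placebo injections with stable NSAIDs 4/32 = 12.5%.

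**Step 3. Effect on an AE rate ratio.** Let R be the rate ratio against placebo in Weeks 4-16, R0 the ratio in Weeks 0-4, and w the placebo-arm AE rate in Weeks 0-4 divided by that in Weeks 4-16. Then

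observed ratio = (4·w·R0 + 12·R) / (4·w + 12).

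R, R0 and w are assumptions; the documents give no AE timing. With R0 = 1:

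| R | w = 1: (4 + 12R)/16 | w = 2: (8 + 12R)/20 |
|---|---|---|
| 0.5 | 0.63 | 0.70 |
| 0.7 | 0.78 | 0.82 |
| 1.5 | 1.38 | 1.30 |
| 2.0 | 1.75 | 1.60 |

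R0 = 1 is what the design implies for the early arm, since both it and the placebo arm then have placebo injections and stable NSAIDs. In the delayed arm R0 reflects secukinumab at unreduced NSAID dose and need not be 1. For example, R0 = 1.5, R = 1 and w = 1 give (6 + 12)/16 = 1.125, a difference that does not come from the tapering weeks.

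**Step 4. Laboratory data.** Protocol Table 6-1 schedules post-baseline chemistry and haematology to Week 16 at Weeks 2, 4, 8, 12 and 16. Blood is drawn before dosing (Protocol 6.5), so Weeks 2 and 4 are stable-NSAID samples: 2 of 5. By-visit summaries keep them apart; maximum or worst value per period does not.

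**Step 5. ECG.** Table 6-1 places ECGs at screening and Week 12, but the values stay at site and SAP 2.8.4.1 plans nothing. Later ECG findings reach the database only as adverse or serious adverse events (Protocol 6.5.7).

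**The case against.** Several points on the other side stand.

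- A reader might infer that no planned safety table is confined to tapering time. That is too broad. The after-Week-16 AE table contains no stable-NSAID weeks, and the by-visit laboratory and vital-sign summaries are not pooled. What is missing is a placebo-controlled AE table under tapering.
- A reader might infer that stable NSAID dosing is compulsory in Weeks 0-4. The wording is advice and a should-statement, although SAP 5.6 lists departure from it as a deviation (COMD10).
- A reader might infer that the objective cannot be answered. Twelve of the 16 weeks are tapering time, and AE start and end dates are collected (Protocol 7.1). The supportable statement is that the tables are diluted and not specific to the objective.
- It is tempting to size the problem from the MEASURE 2 Week 16 AE incidences (65.3% on 150 mg, 63.5% on placebo; Protocol 3.6) under a constant hazard. With h = -ln(1 - 0.653)/16, 1 - exp(-4h) = 23.2%, so 23.2/65.3, about 36%, of patients with an AE would have their first one before Week 4. This does not show dilution. The arm difference is 65.3 - 63.5 = 1.8 points over Weeks 0-16 and 54.8 - 53.0 = 1.8 points over 12 weeks. It also counts first events only, and it does not describe the early arm, which is on placebo injections in Weeks 0-3.
- Tapering is voluntary, so a Week 4-16 window still mixes patients who reduced NSAIDs with patients who did not. This limits what the fix can deliver, but that window is closer to the objective than Weeks 0-16.
- The ECG mismatch changes no result, because no ECG table is planned and reported findings count as AEs.

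**Conclusion.** The point holds in a limited form. A quarter of the Week 1-16 AE window is time in which NSAIDs should be stable, and for the early arm that quarter is also without secukinumab. The planned AE table free of such time has no placebo control. AE contrasts under tapering are pulled toward no difference when the arms do not differ in Weeks 0-4: for example 2.0 becomes 1.75, or 1.60 if the placebo AE rate is twice as high in those weeks. These sizes rest on assumed rates and full follow-up; the 25% rests only on the schedule. Worst-value laboratory summaries share the problem, while by-visit summaries do not. The ECG wording is a plain inconsistency between the endpoint, the data capture rules and SAP 2.8.4.1.

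The objective is exploratory and outside H1 to H11, so no confirmatory conclusion is at risk. This is a cheap improvement to a descriptive analysis.

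**What to change.** 1. In SAP 2.8.1, add AE summaries, crude and exposure-adjusted, by randomised arm for events with onset from Week 4 to Week 16 pre-dose. Use their own denominator (patients still in the study at Week 4) and exposure time. Place them next to a Weeks 0-4 summary.
2. In SAP 2.8.3, split the maximum-change, extreme-shift and worst-grade summaries at the same point, with the Week 4 sample in the first window. Keep the pre-treatment baseline. Re-basing at Week 4 would set the delayed arm's baseline after four secukinumab doses and the early arm's before its first.
3. Label Weeks 4-16 as time when tapering is allowed, not as reduced intake.
4. Delete ECG values from the Table 1.2-1 endpoint, or state that ECG findings count only as AEs. Align the ECG example in SAP Table 2-2.
5. Keep all existing tables.

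No new data are needed. The cost is SAP wording and a few tables with fewer events each. The Week 4 denominator leaves out patients who left earlier, so their number per arm should be shown.
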